**Table JAIN.6.9. Description of Primary, Secondary, and Exploratory Efficacy Analyses (Period 3 and Period 4)**

Measure	Variable	Population (Section 6.2.1)	Analysis Method (Section 6.2.2)	Time Point	Baseline definition
Validated Investigator's Global Assessment for AD (IGA)	Proportion of patients with a response of IGA 0 or 1	LTE Substudy Population	Descriptive using Obs and mLOCF	Weeks 52-200	N.A.
		LTE Substudy Population – Patients with IGA of 0 or 1 at Week 52	Descriptive using Obs and mLOCF	Weeks 52-200	
		LTE Non-responder Population	Descriptive using Obs and mLOCF	Weeks 52-200	
	Proportion of patients with a response of IGA 0, 1, or 2	LTE Responder & Partial Responders who did not enter the substudy	Descriptive using Obs and mLOCF	Weeks 52-200	
	Time to relapse (time to IGA $\geq 3$ )	LTE Substudy Relapse Population	
 
Descriptive
 
Kaplan-Meier plot
 
	Downtitration and withdrawal period	N.A.
	Proportion of patients with a response of IGA(0, 1), IGA(0, 1, 2) within 16 weeks of Disease Retreatment	LTE Substudy Relapse Population	Descriptive	Downtitration and withdrawal period	N.A.
Eczema Area and Severity Index (EASI)	Proportion of patients achieving EASI75 (achieving EASI percent change from baseline $\leq -75$ )	LTE Substudy Population	Descriptive using Obs and mLOCF	Weeks 52-200	Week 0 Baseline
		LTE Substudy Population - Patients with IGA of 0 or 1 at Week 52	Descriptive using Obs and mLOCF	Weeks 52-200	Week 0 Baseline
		LTE Non-responder Population	Descriptive using Obs and mLOCF	Weeks 52-200	Week 0 Baseline

Measure	Variable	Population (Section 6.2.1)	Analysis Method (Section 6.2.2)	Time Point	Baseline definition
	Proportion of patients achieving EASI50	LTE Responder & Partial Responders who did not enter the substudy	Descriptive using Obs and mLOCF	Weeks 52-200	Week 0 Baseline
	Proportion of patients achieving EASI90				
Eczema Area and Severity Index (EASI)	Change from baseline in EASI score	LTE Substudy Population	Descriptive using Obs and mLOCF	Weeks 52-200	Week 0 Baseline
	Percent change from baseline in EASI score	LTE Substudy Population – Patients with IGA of 0 or 1 at Week 52	Descriptive using Obs and mLOCF	Weeks 52-200	Week 0 Baseline
		LTE Non-responder Population	Descriptive using Obs and mLOCF	Weeks 52-200	Week 0 Baseline
		LTE Responder & Partial Responders who did not enter the substudy	Descriptive using Obs and mLOCF	Weeks 52-200	Week 0 Baseline
Eczema Area and Severity Index (EASI)	Proportion of patients achieving absolute EASI $\leq$ 7	LTE Substudy Population	Descriptive using Obs and mLOCF	Weeks 52-200	N.A.
		LTE Substudy Population – Patients with IGA of 0 or 1 at Week 52	Descriptive using Obs and mLOCF	Weeks 52-200	N.A.
		LTE Non-responder Population	Descriptive using Obs and mLOCF	Weeks 52-200	N.A.
		LTE Responder & Partial Responders who did not enter the substudy	Descriptive using Obs and mLOCF	Weeks 52-200	N.A.

Abbreviations: AD = atopic dermatitis; EASI50 = 50% improvement from baseline in Eczema Area and Severity Index score; EASI75 = 75% improvement from baseline in Eczema Area and Severity Index score; EASI90 = 90% improvement from baseline in Eczema Area and Severity Index score; IGA = Investigator's Global Assessment for AD; LTE = Long-Term Extension; mLOCF = modified last observation carried forward; N.A. = not applicable; Obs = Observed.

Notes: missing data related to COVID-19 may be imputed using the method specified in Section 6.3.7.

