8.2. Discontinuation from the Study

Patients will be discontinued in the following circumstances:

- enrollment in any other clinical study involving an investigational product or enrollment in any other type of medical research judged not to be scientifically or medically compatible with this study
- participation in the study needs to be stopped for medical, safety, regulatory, or other reasons consistent with applicable laws, regulations, and good clinical practice (GCP)
- investigator decision
 - the investigator decides that the patient should be discontinued from the study
 - if the patient, for any reason, requires treatment with another systemic therapeutic agent (not allowed as part of rescue therapy [Section 7.7.5]) that has been demonstrated to be effective for treatment of the study indication, discontinuation from the study occurs prior to introduction of the new agent.

Note: Patients rescued to systemic therapies prior to the primary endpoint (Week 16) will be encouraged to continue with study visits and assessments through Visit 8.

- subject decision
 - the patient requests to be withdrawn from the study.
- study termination may occur in a specific country or region when baricitinib is approved for the treatment of AD and becomes reimbursed or commercially available in that country or region, or a negative regulatory opinion is received in that country or region.

Patients discontinuing from the study prematurely for any reason should complete adverse event and other safety follow-up per Section 2 (Schedule of Activities), Section 9.2 (Adverse Events), and Section 9.4 (Safety) of this protocol.

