Missingness due to COVID-19	Section 6.3.7	Added a sentence about not implementing a special missing imputation method if the missing data due to Covid-19 does not exceed 5%.
Patient Disposition	Section 6.5	Added disposition summary for Period 3 and Period 4.
Treatment Compliance	Section 6.7	Added compliance and exposure summary for Period 3
Extent of Exposure	Section 6.13.1	
Background Therapy	Section 6.8	Added TCS summary for Period 3
Efficacy Analyses	Section 6.10	Added a paragraph for Period 3 Efficacy analyses description
Description of Efficacy analysis	Table 6.7 and Table 6.9	Modified the table to include all Efficacy measurements analyses for Week-104 DBL

Change	Section	Summary of Change
Safety Analysis Populations	Table 3.1	Added LTE populations for Period 3 Safety analyses
Safety Analyses	Section 6.13	Added the scope of safety analyses for the Week-104 interim lock

Statistical analysis plan (SAP) Version 5 was approved prior to final DBL. Baricitinib is approved for moderate-to-severe Atopic Dermatitis in over 50 countries. Based on widespread approval, Lilly have made the decision to begin closure of sites in countries where there is regulatory approval and reimbursement. This is being rolled out in a phased” approach based on country approval and accessibility. Patients have been rolled off following confirmation that baricitinib is available locally. Individual unblinding has been provided to guide transition to commercial product while blinding has been maintained for patients remaining in the trial. All unblinding occurred after Week 104 DBL. The protocol did not include any primary or secondary endpoints beyond Week 104 and there was no critical regulatory commitments or publications that would warrant preservation of the blind until the final DBL.

This version of the SAP pertains to the analysis at Final DBL. The changes incorporated in Version 5 are summarized as follows:

Change	Section	Summary of Change
Table Title	Table 6.1 and Table 6.3	Updated Title. Added Word “Analysis” in the end of Title for Table 6.1. Added word “Final DBL” in the end of the Title for Table 6.3 Upated table content for “Safety Population” of Table 6.3
General consideration for Analyses	Section 6.2.2	Added General consideration for Period 4 (beyond Week 104) analyses
Health Outcomes and Quality-of-Life Measures Analyses	Table 6.12	Updated Timepoint for endpoints Itch NRS , Skin Pain NRS, ADSS, and PGI-S AD

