### **6.2.2. General Considerations for Analyses for the 24-Week, 52-Week, , 104-Week Interim Analysis, and Final DBL**

**Period 2** starts at randomization (Visit 2, Week 0) and ends with the visit at Week 52 (Visit 14) or the early discontinuation visit (between Weeks 0 and 52).

**24-week interim analysis** will be done when all the patients complete Week 24 assessment (Visit 10) or discontinue study or treatment before the Week 24 assessment.

**52-week interim analysis** will be done when all the patients complete Week 52 assessment (Visit 14) or the early termination visit (between Weeks 0 and 52).

**Period 3** starts at re-randomization (Visit 14, Week 52) and ends with the visit at Week 104 (Visit 22) or the early discontinuation visit (between Weeks 52 and 104).

**104-week interim analysis** will be conducted when all the patients complete Week 104 assessment (Visit 22) or the early termination visit (between Weeks 0 and 104).

**Period 4** starts at (Visit 22, Week 104) and ends with the visit at Week 200 (Visit 28) or the early termination visit (between Weeks 104 and 200). For the final DBL, efficacy endpoints beyond week 104 will be exploratory in nature and will be analyzed in a descriptive way using observed data.

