### 6.3. Handling of Dropouts or Missing Data

Intercurrent events (ICH E9 R1) are events which occur after the treatment initiation and make it impossible to measure a variable or influence how it would be interpreted.

Depending on the estimand being addressed, different methods will be used to handle missing data as a result of intercurrent events. Intercurrent events may occur through the following:

- application of one of the censoring rules (including after permanent study drug discontinuation, after rescue therapy, or re-treatment)
- discontinuation of inadvertently enrolled patients

- discontinuation from the study due to enrollment in other trials, medical, safety or regulatory reasons, investigator decision, and patient decision
- missing an intermediate visit prior to discontinuation, rescue, or re-treatment
- loss to follow-up

Noncensor intercurrent events are events that are not due to the application of any censoring rule, that is, the last 4 items in the list above.

Note that as efficacy and health outcome data can accrue after a patient permanently discontinues study drug or begins rescue therapy, specific general censoring rules to the data will be applied to all efficacy and health outcome observations subsequent to these events depending on the estimand being addressed. These specific censoring rules are described below.

The *primary censoring rule* will censor efficacy and health outcome results after permanent study drug discontinuation or after rescue therapy. This censoring rule will be applied to all continuous and categorical efficacy and health outcome endpoints.

A *secondary censoring rule* will only censor efficacy and health outcome results after permanent study drug discontinuation. As a consequence, data for patients rescued with high or ultra-high potency TCS or with phototherapy will not be censored at the time of rescue as they can continue or only temporarily interrupt study drug. As patients who are rescued to systemic corticosteroids are required to permanently discontinue study drug, they will also have post-rescue observations censored. The secondary censoring rule will be applied to primary and key secondary efficacy and health outcome endpoints. The secondary censoring rule will be applied to all endpoints at Week 52 as the main analyses.

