**Table JAIN.6.4. Imputation Techniques for Various Variables**

Efficacy and Health Outcome Endpoints for 24-week interim analyses	Imputation Method
IGA (0,1), EASI75, 4-point Itch NRS improvement	NRI a,b , pMI a , Tipping point a
EASI90, SCORAD75	NRI a,b , pMI a
EASI percent change, ADSS Item 2 change, Skin Pain NRS change	MMRM a,b , mLOCF a , pMI a , mBOCF a
All remaining categorical measures	NRI a
All remaining continuous efficacy and health outcome measures	MMRM a , mLOCF a
Efficacy and Health Outcome Endpoints for 52-week interim analyses	
IGA (0,1), EASI75, 4-point Itch NRS improvement	NRI a,b
EASI90, SCORAD75	NRI b
IGA(0,1,2), EASI <=7, SCORAD <=25, DLQI <=5	NRI a,b
All remaining categorical measures	NRI b
EASI percent change, ADSS Item 2 change, Skin Pain NRS change	MMRM b , mLOCF b
All remaining continuous efficacy and health outcome measures	MMRM b , mLOCF b
Efficacy and Health Outcome Endpoints for Period 3 and/or Period 4 analyses	
IGA (0,1), EASI75, 4-point Itch NRS improvement	mLOCF c
All remaining categorical measures	mLOCF c
EASI percent change, ADSS Item 2 change, Skin Pain NRS change	mLOCF c
All remaining continuous efficacy and health outcome measures	mLOCF c

Abbreviations: ADSS = Atopic Dermatitis Sleep Scale; EASI = Eczema Area and Severity Index score; EASI75 = 75% improvement from baseline in Eczema Area and Severity Index score; EASI90 = 90% improvement from baseline in Eczema Area and Severity Index score; IGA = Investigator's Global Assessment for AD; mBOCF = modified baseline observation carried forward; mLOCF = modified last observation carried forward; MMRM = mixed model repeated measures; NRI = nonresponder imputation, NRS = Numeric Rating Scale; pMI = placebo multiple imputation; SCORAD75 = 75% decrease from baseline in Scoring Atopic Dermatitis values.

Notes: missing data related to COVID-19 may be imputed using the method specified in Section 6.3.7.

a Analyses utilizing the primary censoring rule.

b Analyses utilizing the secondary censoring rule.

c Analyses utilizing the Long-Term Extension Substudy censoring rule, or Long-Term Extension Non-responder censoring rule.

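### SAP Section 6.2.2 limits efficacy after Week 104 to observed data, but Tables JAIN.6.4, 6.9 and the DLQI rows of 6.12 also carry values forward in Period 4, with no exception for patients rolled off when their country closed

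*SAP*

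**What the plan says.** SAP Section 6.2.2 sets the rule for the final database lock: "efficacy endpoints beyond week 104 will be exploratory in nature and will be analyzed in a descriptive way using observed data".

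Three tables say something different about method. Table JAIN.6.4 has a block headed "Efficacy and Health Outcome Endpoints for Period 3 and/or Period 4 analyses", in which mLOCF is the only technique listed for every categorical and continuous endpoint. Table JAIN.6.9 gives "Descriptive using Obs and mLOCF" for the IGA and EASI response and change endpoints, with the time point set at Weeks 52-200. Table JAIN.6.12 gives the same method to Week 200 for DLQI. Its diary endpoints (Itch NRS, Skin Pain NRS, ADSS, PGI-S-AD) stop at Week 68.

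On how patients leave, SAP Section 3 (Version 5) reports a decision to "begin closure of sites in countries where there is regulatory approval and reimbursement" and adds: "Patients have been rolled off following confirmation that baricitinib is available locally". Protocol Section 8.2 provides for this: "study termination may occur in a specific country or region when baricitinib is approved for the treatment of AD", subject to reimbursement or commercial availability there. Among the intercurrent events, SAP Section 6.3 lists "discontinuation from the study due to enrollment in other trials, medical, safety or regulatory reasons, investigator decision, and patient decision". Section 6.3.3 carries the last value forward after any intercurrent event and gives a further carry-forward rule for Periods 3 and 4 that depends on dose changes. Neither part mentions closure of a site or country.

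**The concern.** A programmer following Section 6.2.2 would produce observed summaries after Week 104 and nothing else. One following Tables JAIN.6.4, 6.9 and 6.12 would also produce mLOCF summaries out to Week 200. The plan does not say which instruction governs.

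The gap has consequences because many exits in Period 4 may be administrative. A patient transferred to commercial drug at Week 120 would still be counted in the mLOCF display at Weeks 136, 152, 168, 184 and 200. Because closure follows approval and reimbursement, such exits cluster by country. Late mLOCF results would combine frozen values from closed countries with real assessments from open ones, and the mLOCF denominator would not show how few patients were actually seen. Section 6.3.3 justifies mLOCF by assuming that the treatment effect stays the same after the event. For a patient who has left the study for commercial supply, the trial has no data with which to check that.

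**Working it through.** The plan states no figure on this point that could be reproduced. The check is a comparison of texts followed by an illustration.

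**1. Do the passages conflict?** Section 6.2.2 applies to visits after Week 104 at the final lock and names observed data. Table JAIN.6.9 and the DLQI rows of Table JAIN.6.12 apply one method, observed plus mLOCF, to a single range running through Week 200. Table JAIN.6.4 names Period 4 in its block header and lists mLOCF alone. They conflict after Week 104. They do not conflict for Weeks 52-104, which Section 6.2.2 does not restrict, or for the diary rows.

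**2. Does roll-off lead to carry-forward?** Section 6.3 counts leaving the study as an intercurrent event without separating administrative closure, and Section 6.3.3 carries values after any such event. For Periods 3 and 4, Section 6.3.3 conditions carry-forward on dose changes and on the censoring cut-off. The extension-period censoring rules in Section 6.3 refer to stopping study drug, retreatment or dose change. None of these removes a rolled-off patient from later visits.

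**3. How long can a value be carried?** Visits after Week 104 fall at Weeks 120, 136, 152, 168, 184 and 200 (SAP Section 6.2.2.1), which is six visits. A patient last assessed at Week 104 is carried for 200 - 104 = 96 weeks.

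**4. What could this do to a Week 200 rate?** Let R be the share of the analysis set no longer in the study, c the response rate in their carried values, and o the rate observed in those remaining. Then:

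- mLOCF rate = R × c + (1 - R) × o
- difference from the observed display = R × (c - o)

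The documents give none of R, c or o, so all values below are assumptions.

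| R | c = 60%, o = 40% | c = 40%, o = 60% | c = o = 50% |
|---|---|---|---|
| 20% | 12 + 32 = 44% (+4) | 8 + 48 = 56% (-4) | 50% (0) |
| 50% | 30 + 20 = 50% (+10) | 20 + 30 = 50% (-10) | 50% (0) |
| 80% | 48 + 8 = 56% (+16) | 32 + 12 = 44% (-16) | 50% (0) |

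The figures in brackets are percentage-point differences between the mLOCF and observed displays at the same visit. They are not a bias against a known truth. With observed data alone, the carried share after Week 104 is zero.

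**The case against.** The strongest reply is that this is an editorial mismatch with little at stake. Tables JAIN.6.9 and 6.12 already include the observed summary that Section 6.2.2 calls for; mLOCF is a second display beside it. Section 6.10 splits reporting of the substudy and non-responder populations into Weeks 52-104 and Weeks 104-200, so mLOCF to Week 104 and observed data afterwards may be what was meant. Section 6.2.2.3 allows no inferential tests in Periods 3 and 4, and Section 3 says that no primary or secondary endpoint lies beyond Week 104. All of this stands and limits the impact. It does not tell a programmer what to produce after Week 104, and Table JAIN.6.4 offers only mLOCF there.

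A second reply is that observed data have weaknesses too. They lose patients who stopped for lack of efficacy, and those still observed come from the countries left open. That is true, and it is why the number observed should be shown. It is no reason to keep a method that Section 6.2.2 does not provide for after Week 104.

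A third reply is that the regulatory reasons in Section 6.3 are not defined to include country closure, which Protocol Section 8.2 lists separately. That is fair, but Section 6.3.3 excludes no kind of exit, so the label does not change the outcome.

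A reader might infer that carry-forward must flatter long-term efficacy. The documents do not support this. Patients who stop for lack of efficacy are carried as well, one of the populations consists of Week 52 non-responders, and the sign depends on rates that are not given. A reader might also want roll-off censored in the Kaplan-Meier plot of time to relapse. Table JAIN.6.9 assigns that plot to a population that Section 6.2.1 restricts to patients who relapsed, so those rolled off without relapse are not in it.

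**Conclusion.** The contradiction is real and sits in the current SAP text. It covers Table JAIN.6.4, Table JAIN.6.9 and the DLQI rows of Table JAIN.6.12, for visits after Week 104 only. As written, a patient who left because a country closed could contribute one value to as many as six visits over 96 weeks.

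The effect on the results cannot be sized from the documents. The range of -16 to +16 points rests on assumed roll-off shares of 20% to 80% and an assumed 20-point gap, in either direction, between carried and observed response; with no gap there is no shift. What follows without those assumptions is that carried values would stand in for patients who are no longer in the study.

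The impact is confined to exploratory, descriptive Period 4 results. The primary and key secondary analyses, mLOCF for Weeks 52-104 and the diary endpoints to Week 68 are untouched.

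**What to change.** Limit mLOCF to visits through Week 104. In Table JAIN.6.4, add a footnote or split the Period 3/Period 4 block into separate rows. In Table JAIN.6.9 and the DLQI rows of Table JAIN.6.12, split the time point so that observed data alone apply after Week 104, as Section 6.2.2 states.

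For each visit after Week 104, show the number of patients observed by treatment group. Section 6.5 already plans discontinuation reasons for Periods 3 and 4; identify roll-off at site or country closure as a reason of its own, so that readers can tell it from clinical discontinuation.

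The cost is a few table edits and somewhat less programming. The downside is smaller denominators, and so less precise summaries, at the late visits.

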### **6.10.1. Rescue Treatment**

A summary of the initial rescue therapy and the reason for rescue will be produced, as well as a summary of the proportion of patients rescued, by study visit and overall, and by type of rescue therapy (high/ultra-high potency TCS, phototherapy, systemic therapy).

A summary of all rescue therapies will be provided.

### **6.10.2. Primary Outcome and Methodology**

Both EASI score and IGA are commonly used in clinical trials, both for qualifying patients for enrollment and for evaluating treatment efficacy (Langley et al. 2015; Futamura et al. 2016; Bożek and Reich 2017). There is no single ‘gold standard’ disease severity scale for AD; however, IGA scales provide clinically meaningful measures to patients and investigators that are easily described and that correspond to disease severity categories (for example, moderate to severe), and a 75% improvement from Baseline (EASI75) is a commonly used measure of treatment effect in AD clinical trials.

The primary objective of this study is to test the hypothesis that baricitinib 4-mg + TCS or baricitinib 2-mg + TCS is superior to placebo + TCS in the treatment of moderate-to-severe AD, as measured by the proportion of patients achieving EASI75 at Week 16 using the ITT population, and assuming the treatment response disappears after patients are rescued or discontinue from study or treatment. This will serve as the primary estimand. In this estimand, missing data due to the application of the primary censoring rule and the occurrence of other noncensor intercurrent events will be imputed using the NRI method described in Section 6.3.1.

A supplemental estimand is to test the hypothesis that baricitinib 4-mg + TCS or baricitinib 2-mg + TCS is superior to placebo + TCS when evaluating the proportion of patients achieving IGA of 0 or 1 with a  $\geq 2$ -point improvement from baseline at Week 16 using the ITT population, assuming the treatment response disappears after patients discontinue from study or treatment. In this supplemental estimand, missing data due to the application of the secondary censoring rule and the occurrence of other noncensor intercurrent events will be imputed using the NRI method described in Section 6.3.1.

A logistic regression analysis as described in Section 6.2.2.2 will be used for the comparisons. The odds ratio, the corresponding 95% CIs and p-value, as well as the treatment differences and the corresponding 95% CIs, will be reported. Missing data will be imputed using the NRI method described in Section 6.3.1.

Multiplicity controlled analyses will be performed on the primary and key secondary (see Section 6.4) objectives in order to control the overall Type I error rate at a 2-sided alpha level of 0.05. A graphical approach will be used to perform the multiplicity controlled analyses as described in Section 6.4.

